### **III. Subject Participation**

#### **A. Recruitment:**

1. Our team has a record of successful recruitment of smokers that spans three decades. Our team has completed 7 large-scale, NIH-funded trials and recruited over 3,000 smokers in the past decade. Moreover, according to TUKHS patient database, there are over 3,700 smokers with COPD within Family Medicine alone. Based on this history and the available patient population, our enrollment goal of 45 smokers and e-cigarette users is comfortably feasible. Participants will be recruited through clinic (KUMC Department of Family Medicine), community-based efforts (e.g., flyers, face-to-face), and social media platforms including Facebook, Instagram, and Craigslist. Flyers will be placed around KUMC/TUKHS for patients to take. We will use the KUMC HERON and KUMC KUCC C3OD databases and the TMC/O2 electronic medical records to identify smokers. We will then send letters to patients on behalf of physicians (with prior physician approval) informing them of the study. In the letter, participants will be given the option to opt out of future study contact. Potential participants that do not opt out will be contacted by phone to assess interest in study enrollment/eligibility. We will also use the Frontiers registry to identify adult smokers who have agreed to be contacted for research. We will also use radio ads, word of mouth, and our existing pool of participants from prior studies. We will post the study to the KUMC Intranet list of current studies for KUMC employees. Additionally, participants are currently being screened for other research studies conducted by our team. Those who have completed studies or who are ineligible for other studies being conducted will be informed about the current study and offered the opportunity to be screened.
2. Recruitment methods are described above. Recruitment will be conducted by members of the study team. Recruitment will be overseen by [name]. Initial screening will be conducted over the phone and by redcap survey.
3. Advertisements and flyers that will be used for recruitment are attached. Advertisements and flyers will be handed out to potential participants by the study team and will be placed in clinics at KUMC/TUKHS.

4. Letters sent on behalf of physicians will be mailed directly to patients to inform them of the study. Within one week of mailing letters, study staff will make follow-up calls to patients who did not opt out and offer initial screening.

**B. Screening Interview/questionnaire:** The screening will be conducted by self-report via a redcap survey and eligibility will be verified by phone and at the initial in-person study visit (i.e., final enrollment). Participants will also have the option to complete initial screening completely by phone. The screening questionnaire will address the general inclusion/exclusion criteria as listed above. Only participants who have expressed interest will be screened. Prior to screening, participants will be given a brief overview of the study and informed that we need to collect some information to learn whether they may be eligible for the research. They will be informed that completion of the screening interview is voluntary, and they can discontinue screening at any time. Participants will be asked to provide consent for screening.

**C. Informed consent process and timing of obtaining of consent**

- 1 Consent procedures will be conducted by trained members of the research team. Prior to consent, participants will be provided a detailed and comprehensive overview of study procedures.
- 2 Individuals interested in the proposed study and deemed to be initially eligible will meet the research assistant at the Clinical Research Unit – Rainbow. Each individual will be given a copy of the consent form and as much time as they need to review its contents. After the consent form is read, both the individual and the research assistant will review the consent form together and the potential participant will be encouraged to ask questions. Each individual will be reminded that participation in the study is completely voluntary. The consenting process will take place in a private location.
- 3 We do not anticipate recruitment of subjects with compromised cognitive abilities and/or decisional impairment. However, if questions regarding a participant's ability to provide informed consent arise, [name] will determine whether the subject is able to give informed consent.

**D. Alternatives to Participation:** The alternative to participation is not participating, continuing to smoke cigarettes as usual, obtaining EC on their own, attempting to quit using FDA-approved pharmacotherapy, attempting to quit cold turkey.

**E. Costs to Subjects:** There are no costs to participants. All tests, procedures, and visits are being performed solely for research purposes and are not billable to insurance companies.

**F. How new information will be conveyed to the study subject and how it will be documented:** We have plans to publish data from this study in aggregate but will not provide any individualized feedback to patients.

**G. Payment, including a prorated plan for payment:** Participants will receive \$10 for final screening. Eligible participants who complete study procedures will receive \$50 for each of the human lab visits, and \$20 for each of the week 4 and 8 RCT visits. In addition, participants will be compensated \$10 for the week 12 visit. Participants who complete all study procedures will earn \$210.

**H. Payment for a research-related injury:** N/A

#### **IV. Data Collection and Protection**

**A. Data Management and Security:** Confidentiality will be maintained by assigning each participant a study identification number and numerically coding all data. The association of the ID-code and the participant's name will be kept by [name] in a locked file cabinet. The screening questionnaire and all survey data will be directly entered into RedCap or CRIS and accessible only by study staff. Any paper copies of records will be kept in a locked filing cabinet in offices that are kept locked when unoccupied. Only summaries of group data will be reported in any publications or presentations, with no identification of individuals. Because identifiable information will be collected, participant privacy will be maintained throughout the duration of the study by adhering to the regulations set forth by the HIPAA Privacy Rule. More specifically, identifiable information will not be released without written authorization of the participant. Mobile devices will not be used for data collection or storage. Identifiable data will not be sent outside of KUMC.

**B. Sample / Specimen Collection:** No more than 7 mL of blood will be collected per blood draw (7 mL per draw x 2 draws per visit x 3 visits = 42 mL total during study). All samples will be de-identified and labeled with a study identification number. Blood samples will be aliquoted into two separate vials. Samples will be stored at the Bioanalytical Laboratory at the Rainbow Clinical Research Center. Samples will be accessible only to members of the study team. Results from biomarker analyses will be de-identified and shared only with members of the research team. Any resulting publications will present the data in aggregate; individual participants will not be identified. Samples will be disposed of one month after the final report is sent out to the Principal Investigator.

**C. Procedures to protect subject confidentiality:** Confidentiality will be maintained by assigning each participant a study identification number and numerically coding all data. All biological samples and survey data will be labeled with the study identification number and never with the participant's name or other identifiable information. The association of the ID-code and the participant's name will be kept by [name] in a locked file cabinet and will only be accessible to members of the study team.

**D. Quality Assurance / Monitoring:** All data will be directly entered into our electronic data capture system (i.e., RedCap or CRIS) that contains edit checks to control the quality and completeness of data entry. Completeness of data entry will be automatically verified before each assessment is completed. The electronic data capture system is behind the KUMC secure firewall with role-based access that is HIPAA and human subjects compliant. There are no plans for ongoing third-party monitoring.

## **V. Data Analysis and Reporting**

**A. Statistical and Data Analysis:** The purpose of this pilot is to build a body of preliminary evidence and determine effect sizes for a fully powered R01 trial. To assess Aim 1, we will obtain means and SD for each variable at V1 and V2 and calculate mean change and SD of the change. Given that there is no difference at this stage in single and enhanced training arms, data for these arms will be combined. We will then construct 95% CIs on the change of each of these variables for treated and control groups. Obtain CI on the difference in the change between the two groups on each of these variables which will allow us to determine the short-term impact of training on outcome variables. To assess Aim 2, we will be able to estimate the proportion of subjects that fall into each of the switch patterns across the three treatment groups. Specifically, we will construct CIs on the proportion of predominant EC users. This would give us the data to determine effect sizes for the fully powered R01 trial. We will obtain means and SDs for each variable (i.e., health effects, puff patterns) at Wk0 and Wk12 and calculate mean change and SD of the change. We will then construct 95% CIs on the change of each of these variables for the three arms. We will obtain CI on the difference in the change between the three groups on each of these variables which will allow us to determine the longer-term impact of training on the outcome variables. Given the pilot nature of the study, we have limited ability to assess variables that may affect our

endpoints of interest, but initial correlations and associations will be examined to see if any of the variables (e.g., stratification variables including EC use history, gender) are related to our endpoints of interest.

**B. Outcome:** The primary study endpoint is changes in puff duration from pre- to post-EC training/brief advice between smokers who received brief advice versus EC training (single episode and enhanced EC training arms combined). We hypothesize that smokers who receive EC training will show greater increases in puff duration compared to brief advice, greater reductions in cigarette craving compared to brief advice, and greater increases in nicotine exposure compared to brief advice. Additionally, enhanced EC training will result in the greatest proportion of predominant EC users, the greatest reduction in COPD-related health effects, and the greatest increases in puff duration.

**C. Study results to participants:** Study results will not be shared with research participants.

**D. Publication Plan:** We plan to publish results in appropriate tobacco and public health journals such as *Addiction*, *Tobacco Control*, *Nicotine and Tobacco Research*, etc. In addition, results will be presented at regional, national, and international conferences.

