**Aim 1:** Understand differences in acute (i.e., in-lab) changes in puff patterns (i.e., puff duration), cigarette craving, and nicotine exposure from pre- to post-EC training/brief advice between smokers who received brief advice versus EC training (single episode and enhanced EC training arms combined). Smokers who receive EC training will show greater increases in puff duration compared to brief advice (*H1a*), greater reductions in cigarette craving compared to brief advice (*H1b*), and greater increases in nicotine exposure compared to brief advice (*H1c*).

**Aim 2:** Determine the longer-term impact of EC training and training dose on switch patterns (i.e., % predominant EC users), health effects (i.e., changes in cardiovascular health, functional activity, lung function) and puff patterns. In a dose response pattern, enhanced EC training will result in the greatest proportion of predominant EC users at Wk12 (*H2a*), the greatest improvements in health outcomes at Wk12 (*H2b*), and the greatest increases in puff duration from baseline to Wk12 (*H2c*) followed by single session training and brief advice.

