- c. **Human Lab Visit 1 (1-14 days after Final Screening):** At Human Lab Visit 1, participants will be re-screened according to inclusion/exclusion criteria. Pregnancy exclusion will be confirmed at each visit. They will be instructed to remain nicotine abstinent for 12 hours prior to the visit. Participants will complete CO measurement to confirm tobacco/nicotine abstinence. Participants will be provided with an overview of the study, and complete additional baseline self-report measures. Self-report will be used for EC abstinence, as there is currently no objective, reliable measure to verify non-use of these products within the time the participants will be in the lab. Cigarette smoking will be assessed using the TLFB in which individuals report on number of CPD in the past 7 days. Participants will be provided the device of their choice and pre-filled pod of their preferred e-liquid flavor. Participants will puff ad libitum for 30 minutes to establish baseline topography levels. Throughout the session, pre-intervention puff topography will be measured via a pressure sensor attached to the device/product and by the integrated topography software within the EC. This will not require anything additional of the participant. Blood sampling for changes in nicotine levels will occur at -5 minutes (pre-vaping session) and +30 minutes (immediately post-session). Self-reported levels of cigarette craving and withdrawal will be measured

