using the Tiffany-Drobes Questionnaire on Smoking Urges – brief (QSU-brief) and Minnesota Nicotine Withdrawal Scale (MNWS) pre- and post-session. The mCES will assess subjective effects and sensory experiences at the end of each session. Participant's intentions for future use (e.g., purchase, use) of ECs will be assessed using a 4-item measure. At the end of the baseline vaping session, participants will be randomized and enrolled (stratified on EC history) to one of three study arms in a 1:1:1 fashion: 1) Brief Advice, 2) Single Episode Training, 3) Enhanced EC Training. See the Training Guild for Researcher for specific training. For the Brief Advice study arm, participants will be given brief advice to switch to the EC and basic instructions on use of the EC and refilling pods. Participants will view their topography post-intervention via the Escribe software while they puff. Based on our preliminary data, trained research staff will give feedback on puff parameters shown to differ between complete switchers and switch "failures" – puff duration, flow rate, inter-puff interval, and puff number. The session will last ~30 minutes. For the Enhanced EC training study arm, participants will receive the same training as the Single Episode Training arm. Participants will be asked to set a switch date using the Action Planning form. Participants will take the EC device home and use it as much or as little as they would like before the next visit. Lung function will be assessed via spirometry. At the end of the visit, a 6-minute walk distance (6MWD) test will be done to assess the participant's overall ability to conduct everyday activities. Baseline cardiovascular functioning will be measured using Pulse Wave Velocity, a sensitive measure of arterial stiffness that shows rapid (~1 month) changes with switching to ECs. Baseline beat-to-beat blood pressure will be measured to assess blood pressure and vascular elasticity. Participants will be compensated \$50 for this visit.

- d. **Human Lab Visit 2 / RCT Visit – Week 0 (1-5 days after Human Lab Visit 1):** Human Lab Visit 2 will occur 1-5 days after Human Lab Visit 2. Human Lab Visit 2 will be identical to Visit 1 but will not include any training, 6MWD test, or cardiovascular assessment. The purpose of this visit is to assess changes in topography following training at visit 1. Participants will be compensated \$50 for this visit.

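### Section V.A measures Aim 2 change from Wk0, a visit held after training that omits the walk and cardiovascular tests, instead of from the pre-intervention baseline that H2c names

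*Protocol*

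**What the plan says.** Section V.A sets the Aim 2 change scores: "We will obtain means and SDs for each variable (i.e., health effects, puff patterns) at Wk0 and Wk12". Mean changes, their SDs and 95% CIs then follow for each of the three arms and for the differences between arms.

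Section II.E.2.d attaches the Week 0 label to Human Lab Visit 2: "Week 0 (1-5 days after Human Lab Visit 1". On its content: "Human Lab Visit 2 will be identical to Visit 1 but will not include any training, 6MWD test, or cardiovascular assessment". Its stated purpose is to "assess changes in topography following training at visit 1".

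Other sections put the start point earlier:

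- H2c in section I.A predicts "the greatest increases in puff duration from baseline to Wk12".
- Section II.E.2.c says of Visit 1: "Participants will puff ad libitum for 30 minutes to establish baseline topography levels". It also says: "Baseline cardiovascular functioning will be measured using Pulse Wave Velocity" and "Baseline beat-to-beat blood pressure will be measured to assess blood pressure and vascular elasticity". The 6MWD is done at the same visit.
- Section II.E.1 schedules pulse wave velocity and beat-to-beat blood pressure at baseline and W12, and 6MWD at baseline, W4 and W12.
- Section II.E.2.b takes the baseline CAT at final screening.

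**The concern.** V.A and H2c name different start points for the same hypothesis. Under V.A the start value is measured after the intervention has been delivered.

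For 6MWD, pulse wave velocity and beat-to-beat blood pressure, the instruction cannot be carried out, so an analyst would notice. For puff duration the problem could pass unnoticed. Visit 2 topography exists, so V.A yields a plausible number, but one that answers another question: what happened after the acute effect of training had already occurred.

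V.A says the pilot exists to supply effect sizes for a fully powered trial. A contrast and an SD of change taken from the wrong start point would feed directly into that design.

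**Working it through.** **1. Which visit is Wk0?** V.A itself uses V1 and V2 for Aim 1, and Wk0 and Wk12 for Aim 2. Section II.E.2.d equates Week 0 with Visit 2. Sections II.B and II.E.2.c deliver the training or advice at Visit 1. Wk0 is therefore post-intervention. The other zero label, Day 0 for final screening (II.E.2.b), does not rescue the text: no puff topography, 6MWD or cardiovascular test is listed there.

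**2. Which Aim 2 measures have a value at each point?**

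| Measure | Pre-Week 0 value called baseline or scheduled as such | Wk0 (Visit 2) |
|---|---|---|
| Puff duration | Visit 1 | yes, after training or advice |
| 6MWD | Visit 1 | excluded by text |
| Pulse wave velocity | Visit 1 | excluded by text |
| Beat-to-beat blood pressure | Visit 1 | excluded by text |
| Spirometry | Visit 1 | not excluded by text |
| CAT | final screening | not mentioned for Visit 1 or Visit 2 |

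Three measures have no Wk0 value by explicit wording.

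**3. What the Wk0 reference does to puff duration.** For any training arm against brief advice,

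Wk0-to-Wk12 contrast = (V1-to-Wk12 contrast) − (V1-to-V2 contrast).

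Let g be the acute training-minus-advice gain from V1 to V2. The shift is then −g. If a fraction r of g is still present at Wk12, the V1-based contrast is r·g and the Wk0-based contrast is (r − 1)·g.

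- r = 1 (gain fully kept): V1-based g, Wk0-based 0, for every g.
- r = 0.5 (half kept): V1-based +0.5g, Wk0-based −0.5g. A lasting benefit would appear with the opposite sign.

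**4. Scale against the planned precision.** Inputs from section II.C.3 are 1.5 s per puff (read as the SD of change, stated over two weeks) and 15 complete cases per arm. The plan's own margins reproduce with the normal approximation:

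- n = 15: 1.96 × 1.5/√15 = 0.76
- n = 30: 1.96 × 1.5/√30 = 0.54

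For a difference between two arms of 15, assuming the same SD holds to Wk12:

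- SE = 1.5 × √(2/15) = 0.548 s
- 95% half-width = 2.048 × 0.548 = 1.12 s (t, 28 df; 1.07 s with z)

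The documents give no g, so the values below are illustrations only.

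| Assumed g (s) | Shift (s) | Shift / 1.12 s half-width |
|---|---|---|
| 0.5 | −0.5 | 0.45 |
| 1.0 | −1.0 | 0.89 |
| 1.5 | −1.5 | 1.34 |

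**5. Enhanced versus single training.** The shift is −(gE − gS), where gE and gS are the two arms' V1-to-V2 gains. It is 0 in expectation if both arms have had the same training by Visit 2, as II.C.3 and V.A say. Section I.A lists a day 3 session for the enhanced arm. If that is counted from Visit 1 (an assumption), Visit 2 on day 4 or 5, that is 2 of the 5 permitted days, would follow it.

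**6. Does Aim 1 already supply the missing piece?** Only in part. V.A reports the V1-to-V2 change with the two training arms combined. Adding published means would not give three-arm baseline-to-Wk12 changes with their SDs and CIs.

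**The case against.** The best defence is that V.A divides time coherently: V1 to V2 for the short-term effect, Wk0 to Wk12 for the longer-term effect. Section II.B does start the 12-week supply and switching support after the second lab visit. For puff patterns, then, a Wk0 start is a meaningful quantity. That stands, but it is not the quantity in H2c, and it gives no start value for three health measures.

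A second defence is that the health measures correct themselves, because sections II.E.1 and II.E.2.c make the intended baseline plain. That is fair: no data are lost, and the practical risk of a wrong number lies mainly with puff duration, a secondary hypothesis in an estimation-only pilot. Visit 1 topography is held for each participant, so the baseline-to-Wk12 change can be recovered. It still leaves V.A stating the wrong visit.

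Two further points limit the size of the claim. The values of g have no source in the protocol, and the SD is stated for two weeks, so the ratios show scale and are not estimates. The day 3 possibility is weak: the visit procedures schedule no such session, II.C.3 and V.A treat the two training arms as alike in the acute phase, and section II.F.1 allows no more than two study visits in seven days, which an in-person session between Visits 1 and 2 would break. The conclusion does not depend on it.

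**Conclusion.** The concern holds. V.A fixes a post-intervention visit as the start of the Aim 2 changes, against H2c and the protocol's own visit schedule. As written, 6MWD, pulse wave velocity and beat-to-beat blood pressure have no start value, and the puff-duration contrasts of training with brief advice are shifted by −g. The existence and form of the shift follow from the text and an identity. Its size is unknown, because g is not given.

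The primary endpoint (V1 to V2 change in puff duration) and the proportion of predominant EC users under H2a are not affected. Enhanced versus single training is unaffected in expectation if the two arms have had the same training by Visit 2. This should be fixed before analysis. It does not threaten the conduct of the trial.

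**What to change.** In V.A, replace Wk0 as the reference for the Aim 2 changes with the pre-intervention measurement: Human Lab Visit 1 for puff topography, spirometry, 6MWD, pulse wave velocity and beat-to-beat blood pressure, and final screening for CAT. If the Week 0 to Week 12 change in puff patterns is also of interest, it can be reported as an additional, separately labelled quantity.

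Because this relies on Visit 1 being a true baseline, reconcile the order of events there. Section II.C.1 randomises after baseline data collection. Section II.E.2.c randomises after the vaping session and describes spirometry, 6MWD and the cardiovascular tests after the training. Section II.B places training at the end of the visit. One sentence should make clear that all Visit 1 baseline tests precede randomisation and training.

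The cost is the wording in V.A and that clarification. The Visit 1 and screening values are already planned, so no visits, procedures or participants are added.

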Our long-term goal of our research is to decrease tobacco-related disease burden among high-risk smokers unable to quit using standard methods. The overall objective of this application is to evaluate the impact of EC training on changes in puff patterns, nicotine craving and exposure, cigarette smoking, and improvements in COPD-related health effects among smokers with COPD who have been unable to quit smoking using pharmacotherapy. Our central hypothesis is that training on optimal puff behavior with ECs (compared to brief advice to switch to ECs) will result in a greater proportion of patients predominantly using ECs and a greater reduction in COPD-related health effects. Furthermore, greater dose of intervention will result in amplified effects. Our central hypothesis has been formulated on the basis of our preliminary data, which suggest that 1) smokers with COPD have a particularly difficult time quitting, 2) smokers with COPD have high levels of interest in using ECs, and 3) predominant EC users engage in distinct puff patterns compared to continued smokers; this puff pattern can be 'trained' and results in higher rates of switching to EC.

Smokers with COPD, stratified by EC naïve and current dual users, who are unwilling to make a pharmacotherapy-assisted quit attempt but that are willing to use ECs will be randomly assigned to receive 1) brief advice to switch to ECs at baseline, 2) a single session of training on optimal EC puffing and use at baseline, or 3) enhanced EC training on optimal EC puffing and use at baseline, day 3, and wks 4, 8, and 12. Participants will complete a human laboratory assessment of EC use patterns and a complementary 12-week RCT of real-world smoking and EC use patterns. The human lab trial will be conducted over two visits to assess acute changes in puff patterns and nicotine craving and exposure. The RCT will provide real-world data on changes in cigarette smoking, COPD-related health effects, and EC puff patterns.

1. Our specific aims are:

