## II. Research Plan and Design

**A. Study Objectives:** The overall objective of this application is to evaluate the impact of EC training on changes in puff patterns, nicotine craving and exposure, cigarette smoking, and improvements in COPD-related health effects among smokers with COPD who are unable to quit smoking using pharmacotherapy.

**B. Study Type and Design:** The proposed study is an open label randomized clinical trial of EC training and training dose among smokers with COPD. Smokers with COPD (n=45) stratified by EC use history (naïve vs. current use) will be randomized (1:1:1) to receive brief advice to switch to ECs, single session EC training, or enhanced EC training. Participants will complete an in-lab assessment of pre-intervention EC puff patterns followed by intervention and a follow-up assessment of resultant changes in EC puff patterns. Visits will be separated by a standard minimum 24-hour washout period. Participants will complete a final assessment of EC puff patterns at Wk 12. Immediately following completion of the second human lab visit, participants will receive 12 weeks of EC and assistance with switching, based on treatment allocation. Participants will complete in-person follow-up assessments throughout the 12-week switch period and those in the enhanced training arm will receive ongoing training.

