### C. Sample size, statistical methods, and power calculation

1. 45 eligible smokers with COPD will be stratified by EC use history (naïve vs. current use) and randomized (1:1:1) to receive brief advice to switch to ECs, single session EC training, or enhanced EC training. Randomization will be determined by computer-generated random numbers. After baseline data collection has been completed, the research assistant will select the sequential study ID number to determine the randomization assignment.
2. This is an open-label trial. There is no blinding involved.
3. Based upon preliminary data, the standard of change in puff duration over two weeks was 1.5 seconds per puff. Assuming a common standard deviation across groups, 15 participants will allow us to obtain a 95% CI with a margin of error of 0.76 for the mean change for brief advice. In the acute phase (i.e., human lab visits 1 and 2), the single episode and enhanced EC training arms will have the same amount of intervention and will be combined. Thus, 30 participants will allow us to obtain a 95% CI with a margin of error of 0.54 for the mean change in puff duration in the combined intervention groups. We also wish to estimate the proportion of subjects who are predominant or complete switchers at Week 12. Fifteen participants in each group will allow us to estimate the 95% CI for the proportion of switchers in each group with a margin of error no greater than 0.25. This data will allow us to determine the sample size needed for a fully powered randomized trial. For the purposes of the current study, we will need 15 complete cases for each group. Due to potential attrition, we will recruit up to 22 participants per group. We will discontinue recruitment when we have 15 complete cases per group.

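### The between-arm comparisons use change scores with no adjustment for the Visit 1 value or the EC-history stratum, so the intervals are wider than they need be

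*Protocol*

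**What the plan says.** Every description of randomisation in the protocol names one stratification factor. The aims section (I.A) has "Smokers with COPD, stratified by EC naïve and current dual users", the sample size section (II.C) has "45 eligible smokers with COPD will be stratified by EC use history", and the Visit 1 procedures (II.E.2) say "participants will be randomized and enrolled (stratified on EC history) to one of three study arms in a 1:1:1 fashion". The design section (II.B) agrees.

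Section V.A then sets out the analysis. For Aim 1 it takes means and SDs at Visits 1 and 2 and forms the change. The first intervals are within group: "We will then construct 95% CIs on the change of each of these variables for treated and control groups". The arm comparison follows: "Obtain CI on the difference in the change between the two groups on each of these variables". Aim 2 repeats this for the three arms, with Week 0 and Week 12 as the two time points. Neither comparison carries a term for the starting value or for EC history.

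EC history appears only at the end of V.A, where exploratory correlations with the endpoints are proposed for variables such as "stratification variables including EC use history, gender". No other section stratifies by gender.

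**The concern.** The protocol stratifies the allocation on EC history and measures puff duration in a vaping session before allocation, but its stated comparison uses neither to sharpen the estimate. A change score fixes the coefficient of the Visit 1 value at 1. Unless the true within-arm slope of Visit 2 on Visit 1 is 1, that leaves avoidable noise in the comparison.

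This matters because V.A gives the pilot's purpose as determining effect sizes for a fully powered trial. The width of the interval on the primary difference is therefore a main product of the study.

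**Working it through.** **Inputs.** From II.C: SD of change in puff duration 1.5 s per puff; 15 participants in brief advice; 30 in the two training arms combined. The protocol's text reads ‘standard of change’, taken here as standard deviation. It was observed over two weeks, whereas Visit 2 falls 1 to 5 days after Visit 1 (II.E.2), so its use for the primary contrast is itself the protocol's assumption. The protocol does not give the Visit 1 to Visit 2 correlation r, or how well EC history predicts change. Both are shown as ranges.

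**Step 1. Reproduce the plan's figures.** With the normal quantile, margin = 1.96 × SD / √n.
- n = 15: 1.96 × 1.5 / √15 = 0.76 s (stated 0.76).
- n = 30: 1.96 × 1.5 / √30 = 0.54 s (stated 0.54).

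Both are margins for a single group. The protocol gives none for the difference, which is the primary endpoint.

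**Step 2. Margin for the primary difference in change.** With t on 43 degrees of freedom, 2.017:

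2.017 × 1.5 × √(1/15 + 1/30) = 2.017 × 1.5 × 0.3162 = 0.957 s.

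**Step 3. Effect of adjusting for Visit 1 puff duration.** Let the variance be σ² at both visits (assumed).
- Variance of the change: 2σ²(1 − r).
- Residual variance after regression on the Visit 1 value: σ²(1 − r²).
- Ratio: (1 − r²) / [2(1 − r)] = (1 + r)/2, so the margin is multiplied by √((1 + r)/2).

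Holding the SD of change at 1.5 s:

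| Assumed r | Factor | Margin (s) |
|---|---|---|
| 0.3 | 0.806 | 0.957 × 0.806 = 0.77 |
| 0.5 | 0.866 | 0.957 × 0.866 = 0.83 |
| 0.7 | 0.922 | 0.957 × 0.922 = 0.88 |

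The margin is thus about 19%, 13% or 8% narrower. The gain shrinks to nothing as r approaches 1. The price in degrees of freedom is negligible: one extra term that explains nothing moves the margin only from 0.9566 to 0.9573 s.

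**Step 4. The stratum, considered separately.** If EC history alone were added and explained a fraction R² of the variance of change, the margin would be 2.018 × 1.5 × √(1 − R²) × 0.3162.

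| Assumed R² | Margin (s) | Simulated coverage of the unadjusted 95% interval |
|---|---|---|
| 0 | 0.96 | 95.1% |
| 0.1 | 0.91 | 96.3% |
| 0.2 | 0.86 | 97.2% |
| 0.3 | 0.80 | 98.3% |
| 0.4 | 0.74 | 99.0% |

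Coverage comes from 20,000 simulated trials, with allocation balanced within two strata of assumed sizes 24 and 21. The adjusted interval stayed at about 95% throughout. The unadjusted interval is therefore conservative if EC history matters, and correct if it does not. The gains in Steps 3 and 4 should not be multiplied together, because part of any stratum effect may already be carried by the Visit 1 value.

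**The case against.** The strongest reply is that covariate adjustment is commonly left to the statistical analysis plan, which is not at hand, and that V.A nowhere forbids it. The protocol also has reasons for change scores: its precision figures rest on the SD of change, obtaining that SD is part of the pilot's purpose, and in a randomised comparison the difference in mean change is a sound estimate. Much of this stands. It makes the point an improvement to a stated method, not the correction of an error. It does not remove the point, because V.A is not silent: it describes the comparison step by step and gives EC history only an exploratory role.

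A reader might infer more than the documents support:
- **That the planned analysis is biased or has inflated error rates.** It is unbiased, and at worst its intervals are too wide.
- **That randomisation is confused over gender.** The aims, design, sample size and procedures sections all give EC history alone. The gender wording sits in an exploratory example, could be read as a separate list item, and changes no result.
- **That EC-naïve and dual users are expected to differ in puff duration, so the stratum must help.** The protocol does not say so. Its background (I.B) contrasts exclusive users with naïve and dual users taken together. A difference in starting level would in any case be subtracted from a change score; the stratum matters there only if it predicts the change.
- **That the 0.77 to 0.88 s range measures the cost of omitting the stratum.** It measures baseline adjustment only.

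**Conclusion.** The point holds as an inexpensive gain in precision. The comparison in V.A is valid but less precise than the collected data allow. The primary margin of 0.96 s would fall to about 0.77 to 0.88 s over assumed correlations of 0.7 down to 0.3 (0.88 s at 0.7, 0.77 s at 0.3), given equal variances and the protocol's SD of 1.5 s. What the EC-history stratum would add cannot be stated from the protocol and could be zero. The gender label is a minor slip of wording.

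**What to change.** 1. In V.A, estimate the primary difference by ANCOVA of Visit 2 puff duration on arm (combined training against brief advice), Visit 1 puff duration and EC-history stratum, with its 95% confidence interval.
2. Use the same form for the continuous Week 12 outcomes, with the pre-randomisation value (screening or Visit 1) as the baseline. Do not use Week 0: it is Human Lab Visit 2, which follows training, so adjusting for it would remove part of the effect being estimated. II.C places allocation after baseline data collection, but the Visit 1 procedures describe spirometry, the walk test and the vascular measures after the allocation step. State that order explicitly, so that it is clear which values precede allocation.
3. Keep reporting the mean and SD of change by arm, which the larger trial needs for planning.
4. Name EC history as the only stratification factor and list gender as a covariate.

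The cost is wording in the analysis section. The measurements and EC history are already collected, and no participants or visits are added.
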